- 2. **Induction phase From Week 0 to 4:** After confirmation of eligibility criteria, participants will start receiving tezepelumab treatment at Visit 2/Week 0 (baseline) and should remain stable on their baseline OCS dose during this phase.
- 3. Oral corticosteroid reduction and maintenance phase From Week 4 to Week 52: Site visits will occur Q4W. Participants will reduce their dosage of OCS according to the schema defined in Table 7 for each baseline OCS dose until they reach the lowest stable OCS dose or until Week 48. The first OCS dose reduction may occur at Visit 3. OCS dose reduction may occur remotely if the scheduled dose reduction does not coincide with a site visit.

Participants will be considered as having reached the lowest stable dose when they have discontinued OCS or no further OCS reduction is possible because of loss of asthma control and/or evidence of AI (as confirmed by morning cortisol test or adrenocorticotropic hormone [ACTH] stimulation test).

Once they reach the lowest stable dose, participants will be considered in maintenance. From Week 48 to Week 52, all participants will remain on their stable daily OCS dose, except if an asthma deterioration or exacerbation occurs. No further down-titration will be allowed from Week 48 onwards.

HPA axis integrity will be evaluated for all participants who have been on 5 mg/day OCS for 4 weeks and prior to any further tapering down the OCS dose (for participants with baseline OCS doses equal to 5 mg/day, this will be assessed 4 weeks after the first dose of tezepelumab administration and before initiation of the OCS reduction and maintenance phase). A screening method with morning serum cortisol (see Section 8.2.1.1) will be done (8 to 9 am morning cortisol level), to evaluate whether the participant has normal cortisol levels or complete AI. Cortisol levels from the morning cortisol test that will be below normal range and above the complete AI range will be considered 'indeterminate' and will require additional testing (ACTH stimulation test or alternative method, as described in Appendix M).

Depending on the morning cortisol level results, the participant will continue per the following guidance:

- Cortisol levels within normal range (Table 9):
 - Participant exhibits absence of signs and/or symptoms of AI: continue OCS down-titration by 2.5 mg Q4W
 - Participant exhibits signs and/or symptoms of AI: continue OCS down-titration at a slower pace (1 mg Q4W)

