8.1 Efficacy Assessments

8.1.1 Assessment of OCS Dose

All participants who meet eligibility criteria and enter the study will receive open-label

tezepelumab during the induction phase (Week 0 to Week 4). During this phase, participants should remain stable on their baseline (Week 0) OCS dose.

During the OCS reduction and maintenance phase, participants will reduce their OCS dose until the participant discontinues OCS or reaches the lowest OCS dose possible. OCS dose reduction may be slowed down in case of a first test result indicating complete AI, an elevated ACQ-6 score, or a first asthma exacerbation. OCS dose reduction will be stopped for the duration of the trial in case of a second test result confirming complete AI or a second asthma exacerbation (details provided in Section 8.1.2, Appendix M, and the schedule provided in Table 7).

No further reductions will be made to OCS dose from Week 48 onwards.

In case of exacerbations, participants will be managed as per details provided in Section 6.5.1.1. Additionally, in case the participant experiences asthma deterioration or an exacerbation, increase in the maintenance OCS daily dose is permitted per investigator discretion. Once the participant recovers from the first asthma exacerbation, further OCS dose reductions will be allowed at a slower pace during the reduction and maintenance phase as described in Table 8. No reductions are allowed after a second exacerbation.

All OCS dose changes, including temporary or permanent interruption of OCS reduction, will be documented in the source documentation and recorded in the appropriate eCRF form, along with reason for change.

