^a Partial AI cortisol testing confirmed with ACTH stimulation testing or the alternative method described in Appendix M. After repetition of the test 2 months later, the decision to further reduce OCS dose will be based on the morning cortisol test results. If test results are normal, the OCS dose may be reduced directly to 0 mg/day (if participant is receiving

^{≤3} mg); the participant will continue receiving 1 mg Q4W if still at risk. If complete AI is indicated, OCS dose will not be modified.
b If morning cortisol test results again indicate complete AI at 3 months, the OCS dose will not be modified as this is the final attempt. If morning cortisol test results indicate risk AI, then reductions will be 1 mg Q4W and, if normal, then reductions will be 2.5 mg Q4W.

Rescue OCS Down-titration After Recovery From the First Event of an Asthma Exacerbation or Deterioration Table 8

Initial OCS dose/day	Rescue OCS down-titration af	ter recovery from an asthma exacerbation	after recovery from an asthma exacerbation or deterioration to reach an OCS dose of:
	10 mg	5 mg	0 mg
> 20 mg	Reduction of 5 mg of the daily dose Q4W until reaching a dose of 10 mg/day	Reduction of 2.5 mg of the daily dose Q4W until reaching a dose of 5 mg/day	No AI: Reduction of 2.5 mg of the daily dose Q4W Partial AI: 1 mg/day of the daily dose Q4W and repeat test 2 months later ^a Complete AI: No OCS dose reduction and repeat test 3 months later ^b
> 10 mg to ≤ 20 mg	Reduction of 5 mg of the daily dose Q4W until reaching a dose of 10 mg/day	Reduction of 2.5 mg of the daily dose Q4W until reaching a dose of 5 mg/day	No AI: Reduction of 2.5 mg of the daily dose Q4W Partial AI: 1 mg/day of the daily dose Q4W and repeat test 2 months later ^a Complete AI: No OCS dose reduction and repeat test 3 months later ^b
> 5 mg to ≤ 10 mg		Reduction of 2.5 mg of the daily dose Q4W until reaching a dose of 5 mg/day	No AI: Reduction of 2.5 mg of the daily dose Q4W Partial AI: 1 mg/day of the daily dose Q4W and repeat test 2 months later ^a Complete AI: No OCS dose reduction and repeat test 3 months later ^b
S mg			No AI: Reduction of 2.5 mg of the daily dose Q4W Partial AI: 1 mg/day of the daily dose Q4W and repeat test 2 months later ^a Complete AI: No OCS dose reduction and repeat test 3 months later ^b

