^a Partial AI cortisol testing confirmed with ACTH stimulation testing or the alternative method described in Appendix M. After repetition of the test 2 months later, the decision to further reduce OCS dose will be based on the morning cortisol test results. If test results are normal the OCS dose may be reduced directly to 0 mg/day (if participant was receiving

 ^{≤ 3} mg); the participant will continue receiving 1 mg Q4W if still at risk.
 b If morning cortisol test results again indicate complete AI at 3 months, the OCS dose will not be modified as this is the last attempt. If morning cortisol test results indicate risk AI, then reductions will be 1 mg Q4W and, if normal, then reductions will be 2.5 mg Q4W.

For prednisone/prednisolone doses below 5 mg, if the exact dose strength is not available in the country, the daily dose to be administered could be achieved by dosing every other day. Daily dose will be the average of 2 days. See Appendix E for help dosing < 5 mg in relation to tablet strength.

8.1.2.1 Asthma Worsening or Exacerbation Preventing OCS Down-titration The OCS dose titration will be interrupted in case of one of the following circumstances related to the asthma condition:

- Asthma deterioration will be assessed by the investigators when there is an increase in ACQ-6 scores of ≥ 0.5 from the value at Visit 2. If the ACQ-6 score at Visit 2 is missing, the 1st score recorded post-Visit 2 and pre-OCS reduction may be used as baseline value for the 0.5-point increase (however, it will not be used to impute the baseline for ACQ-6 analysis). At each visit, in addition to the participant's asthma symptoms, investigators will use the participant's weekly ACQ-6 scores and will further reduce the OCS dose unless asthma control is lost or AI prevents further dose reduction.
- In case of an asthma exacerbation that requires treatment with a temporary bolus/burst of systemic corticosteroids (or a temporary increase in stable OCS background dose) for at least 3 consecutive days², in-patient hospitalisation, or ER admission, the OCS dose titration will be interrupted, and appropriate treatment will be administered as described in Section 6.5.1.1.
- After recovery from the first asthma deterioration or exacerbation, participants will be
 offered to continue OCS tapering down at a slower speed (ie, Q4W). If the first asthma
 deterioration or exacerbation occurs between Week 48 and Week 52, no further
 down-titration will be allowed.

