Appendix M Alternative Method for Hypothalamic-pituitary-adrenal Axis Evaluation

FOR USE ONLY IF TETRACOSACTIDE IS NOT REGISTERED IN YOUR COUNTRY OR WITH PERMISSION FROM LABCORP IF TETRACOSACTIDE IS NOT AVAILABLE AT YOUR SITE

First test (before reducing the maintenance OCS dose below 5 mg per day)

Sample	8–9am cortisol cortisol ^a	Action	Status
1	>350 nmol/L	Continue down-titration (2.5 mg every 4 weeks to zero)	No AI
	100–350 nmol/L	Repeat 8–9am cortisol approximately 1 week later (instead of performing ACTH stimulation test) and interpret according to sample 2 below	Indeterminate
	<100 nmol/L	Delay titration and repeat test in 3 months ^b	Complete AI

Second test - Approximately 1 week after the first test in case the first test was indeterminate

Sample	8–9am cortisol cortisol ^a	Action	Status
2	>350 nmol/L	continue down-titration (2.5 mg every 4 weeks to zero)	No AI
	≤350 nmol/L or when signs or symptoms of AI are present	If serum cortisol ≥250 nmol/L on either sample 1 or sample 2, proceed with slow titration (1 mg every 4 weeks) until the participant reaches a prednisolone / prednisone dosage of 3 mg per day and then repeat testing ^b (ie, at 2 months – see 3 rd test below)	Partial AI
		If serum cortisol <250 nmol/L on both samples 1 and 2, delay titration and repeat test in 3 months ^b (see 3 rd test below)	Complete AI

Third test - 2 or 3 months later (see Section 8.2.1)

[figure not shown]
Sample	8–9am cortisol	Action	Status
	cortisol ^a		
3	>350 nmol/L	Continue down-titration (2.5 mg every 4 weeks to zero)	No AI
	100–350 nmol/L	Repeat 8–9am cortisol approximately 1 week later and interpret according to sample 4 below	Indeterminate
	<100 nmol/L	Delay titration and repeat test in 3 months ^b	Complete AI

Fourth test - Approximately one week after the third

Sample	8–9am cortisol cortisol ^a	Action	Status
4	>350 nmol/L	Continue down-titration (2.5 mg every 4 weeks, or 1 mg every 4 weeks if signs or symptoms of AI are present)	No AI
	≤350 nmol/L or when signs or symptoms of AI are present	If serum cortisol ≥250 nmol/L on either sample 3 or sample 4, continue with slow titration (1 mg every 4 weeks) until the participant reaches a prednisolone / prednisone dosage of 1 mg per day and then repeat testing (ie, at 2 months) and discuss with endocrinologist ^b	Partial AI
		If serum cortisol <250 nmol/L on both samples 3 and 4, delay titration and discuss with endocrinologist	Complete AI

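### Appendix M's third-test row below 100 nmol/L schedules another 3-month repeat for participants already shown to have complete adrenal insufficiency, although Section 8.1.1 and Tables 7 and 8 make that second result final

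*Protocol*

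**What the plan says.** Appendix M replaces the ACTH stimulation test with repeated morning cortisol. It is mandatory in countries where tetracosactide is not registered (Protocol 8.2.1.2) and may be used elsewhere with permission. SAP 4.2.1.7 lists Poland, Bulgaria and Latvia as countries without the ACTH test.

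The third test in Appendix M is headed "2 or 3 months later (see Section 8.2.1)". It therefore receives two groups: participants with partial AI, at 2 months, and participants with complete AI, at 3 months. For a result below 100 nmol/L there is one row, labelled complete AI, and its action is "Delay titration and repeat test in 3 months".

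Three other places in the protocol deal with a second complete-AI result:

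- Section 8.1.1: "OCS dose reduction will be stopped for the duration of the trial in case of a second test result confirming complete AI". The sentence refers the reader to Section 8.1.2, Appendix M and Table 7 for details.
- Table 7, footnote b, on complete AI again at 3 months: "the OCS dose will not be modified as this is the final attempt".
- Table 8, footnote b, in the same situation: "the OCS dose will not be modified as this is the last attempt".

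Neither footnote b is limited to tetracosactide sites. Footnote a of the same tables covers partial AI "confirmed with ACTH stimulation testing or the alternative method described in Appendix M". Section 8.2.1.1 also describes a final attempt, but its action list is for sites with tetracosactide, so this point does not rely on it.

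**The concern.** Take a participant at an Appendix M site who has complete AI at the first evaluation and a cortisol below 100 nmol/L three months later. Under Section 8.1.1 and footnotes b, reduction is over and the participant stays at 5 mg to Week 52. Under the Appendix M row, titration is only postponed and a further test is due, which could reopen the taper.

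Both texts hold the dose on the day of the third test. They differ on what may happen afterwards. Complete discontinuation of OCS is a primary endpoint, so a participant's Week 52 outcome could depend on which text the site followed. The problem sits mainly in one level of the access-to-ACTH-test subgroup that SAP 4.2.1.7 presents for the primary endpoints.

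**Working it through.** **Comparing the texts.** Under Appendix M, complete AI at the first evaluation means sample 1 below 100 nmol/L, or samples 1 and 2 both below 250 nmol/L. Both lead to the third test at 3 months.

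| Arrival at third test | Result below 100 nmol/L is | 8.1.1 and footnotes b | Appendix M row |
|---|---|---|---|
| From partial AI | first complete-AI result | repeat in 3 months | repeat in 3 months: consistent |
| From complete AI | second complete-AI result | no further reduction in the trial | repeat in 3 months: conflict |

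**Could the extra repeat matter before the cut-off?** The limit in Section 4.1 is "No further down-titration will be allowed from Week 48 onwards". Inputs:

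- Table 7 steps at the fastest pace, first reduction at Week 4, no asthma setback.
- First test (T1) after 4 weeks on 5 mg, or at Week 4 for a 5 mg baseline.
- 3 months taken as m = 12 or 13 weeks (assumption).
- Appendix M has no table for a test after the third-test repeat order, so the third-test rows are applied again (assumption). A normal result then means 2.5 mg off that week and 0 mg four weeks later.

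Formulas: third test = T1 + m; extra repeat = T1 + 2m; 0 mg = T1 + 2m + 4. For a 10 mg baseline, 7.5 mg is reached at Week 4 and 5 mg at Week 8, so T1 = 12. The third test is at Week 24–25, the extra repeat at 36–38 and 0 mg at 40–42.

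| Baseline | 5 mg reached (week) | First test | Third test | Extra repeat | 0 mg if normal |
|---|---|---|---|---|---|
| 5 mg | baseline | 4 | 16–17 | 28–30 | 32–34 |
| 7.5 mg | 4 | 8 | 20–21 | 32–34 | 36–38 |
| 10 mg | 8 | 12 | 24–25 | 36–38 | 40–42 |
| 20 mg | 12 | 16 | 28–29 | 40–42 | 44–46 |
| 40 mg | 17 | 21 | 33–34 | 45–47 | 49–51, not allowed |

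If complete AI was established by the second sample about a week later, each later date moves by about one week; from 20 mg, 0 mg would then be at Weeks 45–47, still before Week 48.

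**Which endpoints can move.**

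- OCS dose ≤ 5 mg: no. AI testing starts when the participant is already on 5 mg.
- Discontinuation at Week 28: no. The earliest 0 mg is Week 32.
- Discontinuation at Week 52: yes. Reaching 0 mg by Week 46 leaves 6 weeks, more than the 2 weeks of unchanged dose required by Protocol Table 13.
- Week 52 OCS-reduction secondary endpoints: yes. Reduction if held at 5 mg is 1 − 5/baseline: 0% from 5 mg, 33.3% from 7.5 mg, 50% from 10 mg, 75% from 20 mg, against 100% at 0 mg. The ≥ 50% endpoint flips only for baselines below 10 mg; the reduction category changes at all four doses.

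**Size.** One participant in 300 is 1/300 = 0.33 points. For scale, the plan's half-width of 5.8 points at 50% and n = 300 reproduces as 5.80 by Clopper-Pearson (150/300). The documents give no rate of two complete-AI results, nor of recovery afterwards.

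**The case against.** The strongest reply is that the row orders a test, not a reduction. A site could repeat the cortisol and leave the dose alone, complying with both texts, and Appendix M gives no rule for acting on the extra result. This has some force: the route to 0 mg rests on an assumption. But the row says titration is delayed, which implies that it may resume, whereas Section 8.1.1 says it is stopped for the trial. Reading delay as stop is strained.

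A second reply is that footnotes b do not name Appendix M; only footnote a does, and it concerns partial AI. That is correct, so the footnotes are supporting evidence. The direct link is Section 8.1.1, which cites Appendix M in the sentence that sets the stop rule.

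Third, the effect needs an unusual sequence: an Appendix M site, two complete-AI results, recovery within the next three months and a near-fastest taper. The study tests no hypothesis, and the SAP already shows results by access to the ACTH test. This stands, and it limits the weight of the point.

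A reader might also infer that partial AI at the extra test still leads to 0 mg, at about Week 43 from 7.5 mg or Week 47 from 10 mg, because Table 7 footnote a says "If test results are normal, the OCS dose may be reduced directly to 0 mg/day" for participants on 3 mg or less. The documents do not support that timeline. If the third-test rows are applied again, an indeterminate result goes to the fourth-test rows, where partial AI means 1 mg every 4 weeks until 1 mg is reached, then retesting. With 13-week months, the 10 mg baseline gives 4, 3 and 2 mg at Weeks 39, 43 and 47, and 1 mg would fall at Week 51, past the limit. The 7.5 mg baseline reaches only 1 mg by Week 47. With 12-week months each date is two weeks earlier, and 1 mg from the 10 mg baseline (Week 49) is still too late. That row's own 2-month gloss does not fit a start from 5 mg, so no firm date can be drawn from it.

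**Conclusion.** The row is wrong as written for participants already shown to have complete AI, and correct for those arriving from partial AI. It is a minor inconsistency. It can alter Week 52 discontinuation and the Week 52 OCS-reduction secondary endpoints, at 0.33 points of the overall discontinuation proportion per affected participant. The timings assume the fastest taper, 12 to 13 weeks for 3 months, and reuse of the third-test rows for the extra test.

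Three stronger readings should be avoided. The documents do not allow a total shift to be estimated, because the number affected is not given; it is probably small. The ≤ 5 mg endpoint and Week 28 discontinuation are not at risk by this route. The fourth-test complete-AI row does not contradict the stop rule: it delays titration and calls for discussion with an endocrinologist, and merely omits that reduction ends.

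**What to change.** In the third-test row for results below 100 nmol/L in Appendix M, state that if an earlier test already showed complete AI, this is the final attempt and the OCS dose is not reduced further, and that the 3-month repeat applies only when this is the first complete-AI result.

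If the sponsor does intend an extra repeat at Appendix M sites, write that exception into Section 8.1.1 and footnotes b of Tables 7 and 8 instead, and say how the extra test is to be read.

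The cost is a short protocol clarification, carried in the next amendment with whatever approvals that amendment requires, and a letter to the sites using Appendix M. The SAP needs no change.

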8.2.1 Hypothalamic-pituitary-adrenal Axis Evaluation

For all participants, HPA axis integrity will be evaluated after 4 weeks on 5 mg/day and prior to tapering down the OCS dose (for participants with baseline OCS doses equal to 5 mg/day, this will be assessed 4 weeks after the first dose of tezepelumab administration and before initiation of the OCS reduction phase).

First, a screening method with morning serum cortisol is done (8-9 am morning cortisol level), to evaluate whether the participant has:

- Normal cortisol levels (Table 9)
- Complete AI (Table 9).

Cortisol levels from the morning cortisol test that are below normal range and above the complete AI range are considered 'indeterminate' (Table 9), and require additional testing described below (for sites where tetracosactide is not available or not registered, please see Appendix M).

If the morning cortisol is in the indeterminate range, then the ACTH stimulation test is done within approximately 1 week (see Section 8.2.1.2 for details). The ACTH stimulation test is more specific than the morning cortisol test, and can determine whether the participant has:

- Normal cortisol levels: > 450 nmol/L (> 675 nmol/L for participants taking oestrogen-containing contraceptives)
- Complete AI: < 250 nmol/L (< 375 nmol/L for participants taking oestrogen-containing contraceptives)
- Partial AI: 250 to 450 nmol/L (375 to 675 nmol/L for participants taking oestrogen-containing contraceptives).

For morning serum cortisol and ACTH stimulation tests, hold OCS dose and other concomitant medications that could interfere with cortisol results as follows (see Section 6.5):

- The last OCS dose should be taken \geq 24 hours prior to testing
- Participants must not take ICS (or ICS/LABA if in single inhaler) treatment on the
 morning of the morning cortisol level/ACTH stimulation test (for participants taking a
 once-daily ICS/LABA formulation, eg, fluticasone furoate/vilanterol, participants must
 not take the treatment ≤ 24 hours prior to the morning of the morning cortisol
 level/ACTH stimulation test)
- If a participant requires a short course of macrolides, antivirals, or azoles, there must be a window of ≥ 1 week prior to the testing of cortisol levels.

The process will be as described in Figure 3.

[figure not shown]

Figure 3 Hypothalamic-pituitary-adrenal Axis Evaluation

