8.2.1.1 Morning Cortisol Test

The morning cortisol test will be done in all participants 4 weeks after reaching the 5 mg dose of OCS, and before further dose reductions. It is also done 3 months after a participant has completed a test indicating complete AI.

Serum samples for cortisol will be collected between 8 and 9 am and will be sent to a central laboratory for evaluation.

The following values will be used to define AI status for the morning cortisol test:

Table 9 Cortisol Status

AI status	SI units	Participants taking oestrogen- containing contraceptives
Normal	>350 nmol/L	>700 nmol/L
Indeterminate results	100 - 350 nmol/L	200 - 700 nmol/L
Complete AI	<100 nmol/L	<200 nmol/L

Once the results are available, the site will inform the participant of the results via telephone. For sites where tetracosactides are available, and depending on the result, the actions that will be implemented are as follows:

- If cortisol levels are within normal range and the participant does not exhibit any signs and/or symptoms of AI, the participant will continue OCS down-titration by 2.5 mg Q4W
- If cortisol levels are within normal range but the participant exhibits signs and/or symptoms of AI, then OCS down-titration should continue at a slower pace (1 mg Q4W).
- If cortisol levels are below the normal range and above the complete AI range (indeterminate result), then the participant will be instructed to maintain the current OCS dose and come back to the site within 1 week for an ACTH stimulation test (Section 8.2.1.2)
- If complete AI is confirmed, sites will inform participant that the OCS dose will remain the same without further reduction until there is evidence of recovery from the complete AI without worsening of asthma control. The morning cortisol test and associated clinical assessments (see Table 1) will be repeated 3 months later. After the repeat morning cortisol test, the site will inform the participant based on the results as follows:
 - If morning cortisol results indicate normal cortisol values, then reductions will be 2.5 mg Q4W, and the participant would subsequently move to maintenance at the OCS lowest possible dose
 - If morning cortisol results are indeterminate, then reductions will be delayed further, and the participant would return approximately 1 week later for an ACTH stimulation test:
 - o If normal result after ACTH stimulation (Table 10): reduce by 2.5 mg Q4W then move to maintenance at the lowest possible dose

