8.2.1.2 Adrenocorticotropic Hormone Stimulation Test

The tetracosactide (also known as Synacthen, Cortrosyn, or cosyntropin) ACTH stimulation test will be performed when morning cortisol levels are in the indeterminate range (for sites

where tetracosactide is not available or not registered, please see Appendix M).

Options for sourcing tetracosactide are provided below:

- Acquire Synacthen or Cortrosyn 250 mg for intravenous (IV) or intramuscular (IM) injection locally and submit invoices for reimbursement (preferred option, if possible).
- If the medication is available in your country but the site cannot directly acquire the medications, then Labcorp or AstraZeneca may arrange for delivery to the site.
- If the medication is available in your country, but delivery to the site is delayed, the site may request permission from Labcorp to use the alternative method described in Appendix M.
- Sites in countries where the medications are not registered must use the alternative method in Appendix M.

The following values will be used to define AI status for the ACTH stimulation test:

Table 10 ACTH Stimulation Status

AI status	SI units	Participants taking oestrogen- containing contraceptives
Normal	>450 nmol/L	>675 nmol/L
Indeterminate results	250 - 450 nmol/L	375 - 675 nmol/L
Complete AI	<250 nmol/L	<375 nmol/L

The sites will inform the participant of the morning cortisol results via phone call, and a visit will be scheduled within 1 week for the ACTH stimulation test.

An injection of the fast-acting ACTH stimulant will be given IV or IM. Serum samples for cortisol will be collected between 8 and 9 am and will be sent to a central laboratory for evaluation as follows: a blood sample for serum cortisol will be collected at 0 minutes (before IV or IM injection) and 30 minutes after the IV or IM injection. Peak cortisol response at 30 minutes will be selected to assess AI, and the OCS taper will follow the applicable scenario below:

• If a normal peak cortisol level is demonstrated at 30 minutes, the site will inform the participant via phone call, and the participant will continue OCS dose titration by 2.5 mg Q4W aiming for 0, and subsequently would move to maintenance at the lowest possible OCS dose

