^a NB thresholds must be adjusted upward for women receiving oral oestrogen therapy as per existing protocol.

^b Participants will be educated for symptom awareness of adrenal suppression and use of steroid emergency cards.

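### Appendix M, tests 2 and 4: a repeat morning cortisol below 100 nmol/L still counts as partial AI, and tapering continues, if the sample a week before was 250–350 nmol/L

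*Protocol*

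**What the plan says.** Appendix M applies where tetracosactide is not registered or, with permission, where it is not available at the site. SAP Section 4.2.1.7 lists Poland, Bulgaria and Latvia as countries without the ACTH test.

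**Tests 1 and 3 (single morning cortisol).** There are three rows. Above 350 nmol/L is no AI, 100–350 is indeterminate and leads to a repeat about a week later, and below 100 is complete AI with the action "Delay titration and repeat test in 3 months".

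**Tests 2 and 4 (the repeat).** There are two rows: above 350, and an open-ended row for 350 or less (or signs or symptoms of AI). The second row is split by the pair of values:
- Test 2, partial AI: "If serum cortisol ≥250 nmol/L on either sample 1 or sample 2, proceed with slow titration (1 mg every 4 weeks" until 3 mg/day, then retest at about two months.
- Test 4, partial AI: "If serum cortisol ≥250 nmol/L on either sample 3 or sample 4, continue with slow titration (1 mg every 4 weeks" until 1 mg/day, then retest, with endocrinologist discussion.
- Complete AI in either test: both samples below 250, and titration is delayed.

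**Main text.** Section 8.2.1.1 introduces Table 9 with "The following values will be used to define AI status for the morning cortisol test"; there, complete AI is below 100 nmol/L (below 200 with oestrogen-containing contraceptives). Section 4.1 holds the dose when complete AI is confirmed by Table 9. Table 7 footnote a covers partial AI established by ACTH testing or by the Appendix M method. It bases the two-month decision on morning cortisol and leaves the dose unchanged if that shows complete AI.

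**Safeguard.** Appendix M footnote b: "Participants will be educated for symptom awareness of adrenal suppression and use of steroid emergency cards".

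**The concern.** The same 8–9 am sample carries a different consequence depending on when it is drawn. A first value of 60 nmol/L stops the taper with no second sample. A value of 60 a week after a value of 300 does not stop it. Under the pair rule, 300 then 60 (mean 180) tapers, while 249 then 249 (mean 249) holds.

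In the ACTH pathway an indeterminate screen is resolved by a stimulated value: "Peak cortisol response at 30 minutes will be selected to assess AI". Appendix M has no stimulated value, so a most recent result in its own complete-AI range is outweighed only by an earlier unstimulated one.

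What is at stake is adrenal safety for a very small number of participants at Appendix M sites. Two steps of 1 mg every 4 weeks take a participant from 5 to 3 mg/day (2/5 = 40%) after test 2, or from 3 to 1 mg/day (2/3 = 67%) after test 4, before cortisol is measured again. The label also feeds the exploratory tabulation of partial and complete AI from the repeated morning cortisol (SAP Section 4.2.14.2).

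**Working it through.** **Step 1. Apply the rule as written.** Inputs come from Appendix M and Table 9. Let s1 be the earlier sample, indeterminate by construction (100–350), and s2 the repeat. With s2 at 350 or less, the status is partial AI if max(s1, s2) ≥ 250, and complete AI otherwise. The same rule holds for samples 3 and 4.

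| s1 | s2 | Tests 2/4 | s2 alone, by tests 1/3 or Table 9 |
|---|---|---|---|
| 300 | 60 | Partial, taper 1 mg Q4W | Complete, hold |
| 250 | 99 | Partial, taper 1 mg Q4W | Complete, hold |
| 249 | 99 | Complete, hold | Complete, hold |
| 200 | 60 | Complete, hold | Complete, hold |

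All integer pairs with s1 from 100 to 350 and s2 from 0 to 499 were enumerated. Every pair with s1 of 250–350 and s2 below 100 is labelled partial although s2 alone is complete AI (101 × 100 = 10,100 grid pairs). No pair with s1 below 250 shows this. The grid count shows where the conflict lies, not how often it occurs.

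**Step 2. Look for an override.** Nothing in Appendix M or its footnotes displaces the either-sample rule when the repeat is below 100. The actions listed in Section 8.2.1.1 are limited to sites with tetracosactide. Table 9's definition comes before that limit, and the Section 4.1 hold is not restricted in that way. For test 4, Table 7 footnote a points to a hold. The matching footnote to Table 8 (rescue titration) has no such sentence, so that particular conflict concerns participants on the Table 7 schedule.

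**Step 3. How often.** The documents give no cortisol distribution or week-to-week variability, so both are assumed.

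*Model A.* s1 lies on 100–350 (uniform, skewed high as Beta(2,1), or skewed low as Beta(1,2)), and s2 = s1 + N(0, SD). Then

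P(s1 ≥ 250 and s2 < 100) = ∫ from 250 to 350 of f(s1) · Φ((100 − s1)/SD) ds1.

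| SD (nmol/L) | Uniform | Skewed high | Skewed low |
|---|---|---|---|
| 30 | 0.000% | 0.000% | 0.000% |
| 50 | 0.008% | 0.010% | 0.005% |
| 75 | 0.251% | 0.350% | 0.152% |
| 100 | 1.092% | 1.593% | 0.59% |

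The denominator is indeterminate participants. As a share of those labelled partial AI, this is 0–0.65% at SD 30–75 and 2.3–3.1% at SD 100.

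*Model B.* The true value is lognormal (median 150, 200 or 250 nmol/L, between-person CV 30% or 50%), and both samples carry independent lognormal within-person error. The joint frequency is 0.000% at within-person CV 15%, at most about 0.06% at CV 25%, and about 0.28–0.59% at CV 35%.

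**Step 4. Size.** For every 100 indeterminate participants at Appendix M sites (an illustrative number), Model A gives 0–0.35 people at SD 30–75 and 0.6–1.6 at SD 100.

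**The case against.** The strongest reply is that this is a stated rule and not a hole. Tests 2 and 4 give every pair a status, and the either/both wording is a best-of-two criterion. Its 250 limit equals the complete-AI limit of the ACTH test in Table 10, so a deliberate surrogate is plausible. Tests 2 and 4 also depart from Table 9 in the stricter direction: 249 and 249 is complete AI in Appendix M, while Table 9 calls each value indeterminate. Some order dependence is normal when a screen is followed by a confirmation, and the ACTH pathway has no override for a 0-minute value below 100 either. If Appendix M alone sets status at these sites, Table 9 does not contradict it; if Table 9 applies, Section 4.1 and Table 7 footnote a already support a hold.

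Much of this stands. The rule may be intended, and the 250 limit need not be disputed. But no passage says why an earlier unstimulated value should outweigh a latest one below 100, and the ACTH pathway classifies on a stimulated value that Appendix M lacks. The either-way argument also concedes that a site can find two instructions for one result, at least at test 4. The mismatch with Appendix M's own tests 1 and 3 remains on either reading.

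The safeguards are substantial. Section 8.2.1.3 requires symptom education for partial or complete AI and, without evidence of HPA recovery, warning identification and a medical report covering IM hydrocortisone. It recommends steroid cover under stress, and provides specialist follow-up at end of treatment or sooner. Visits are every 4 weeks, 1 mg Q4W is the slowest taper, adrenal crisis is an AESI, and Section 6.5 requires rescheduling when steroids were not properly withheld. These reduce the risk but do not settle which instruction applies. Only test 4 asks for endocrinologist discussion in the row itself.

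**Conclusion.** The point holds as a low-severity, inexpensive improvement. As written, an earlier sample of 250–350 nmol/L with a repeat below 100 is partial AI and tapers. That is inconsistent with Appendix M tests 1 and 3, with Table 9 and, for test 4, with Table 7 footnote a. The textual finding rests on no assumption. The frequency, about 0 to 1.6 per 100 indeterminate participants, rests entirely on assumed cortisol distributions and variability.

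Three stronger readings are tempting, and the documents do not support them:
- *That the 250 nmol/L limit or the either-sample rule is itself an error.* The rule is explicit and matches a limit used elsewhere; only its behaviour below 100 conflicts with other text.
- *That the oestrogen-adjusted 250 should be 500 nmol/L, because Table 9 doubles its other two limits.* Footnote a says only that "thresholds must be adjusted upward for women receiving oral oestrogen therapy as per existing protocol", and the one adjusted 250 in the protocol is 375, for stimulated cortisol ("Complete AI: < 250 nmol/L (< 375 nmol/L for participants taking oestrogen-containing contraceptives"). The figure 500 would be an extrapolation with a real cost. With the Model A form on 200–700 nmol/L and SD 30–150, moving from 375 to 500 turns about 18–30% of indeterminate oestrogen users from partial to complete AI and stops their taper.
- *That efficacy results are at risk.* At this frequency no primary or secondary estimate would visibly change.

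**What to change.** Add one line to each of tests 2 and 4 in Appendix M: a repeat sample below 100 nmol/L (below 200 nmol/L if taking oestrogen, per Table 9) is complete AI and titration is delayed, whatever the earlier sample. Keep the endocrinologist discussion at test 4. If the sponsor intends the earlier sample to prevail, the alternative is to say so, give the reason, and reconcile Table 7 footnote a.

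The cost is two table rows. Only pairs with an earlier value of 250–350 and a repeat below 100 change status; pairs with an earlier value of 100–249 and a repeat below 100 are already complete AI. The downside is a hold in place of a slow taper for those few participants, which Appendix M already imposes after a single value below 100 at tests 1 and 3. No change to the 250 limit or its oestrogen adjustment is proposed.
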